2.0 STUDY OBJECTIVES

Outcomes:

- Primary outcomes: radiation exposure, time, accuracy of placement (right angle to rod).
 - Each distal interlock will be considered a separate outcome
 - The first fluoroscopy shot to localize the jig or obtain a perfect circle is considered start time. The surgeon will note the hour, minute, and seconds of the time based on the wall clock in the operating room.
 - The last shot to confirm complete seating of the screw will be considered end time. The surgeon will note the hour, minute, and seconds of the time based on the wall clock in the operating room.
- Secondary outcomes:
 - accuracy of placement (right angle to intramedullary nail).
 - Number of complete misses of the nail with the drill or the screw
 - comparison of learning curve between distal targeter and freehand techniques stratified by level of training
 - The level of training of the surgeon
 - Experience level of the surgeon
 - estimated number total number of intramedullary nails placed
 - time since the last intramedullary nail placement
 - estimated number of nails placed per month over the last year
 - number of times the surgeon has used the distal targeting system
 - Comparison of tibia vs femur antegrade nails

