3.5 SUBJECT RECRUITMENT

Patients will be recruited from all full-time orthopaedic trauma faculty. The treating surgeon and/or clinical research associate will approach patients in person to recruit, enroll and consent them for the study. No advertisement will be used for this study.

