7.0 STATISTICAL CONSIDERATIONS

7.1 STUDY OUTCOME MEASURES

- Primary Outcome analysis: 2 tailed T-test for average length of surgery (skin to skin), average time to place 2 interlocks (start time when nail is seated and surgeon states s/he is ready to proceed with distal interlocking screw placement). Average radiation used in microGrays. Femur vs tibia average time to place 2 interlocks and average radiation exposure.
 - To compare time and accuracy of placement only data from surgeons who have performed both DT and FH techniques more than 5 times will be included.
- Secondary outcomes: t-test accuracy of screw placement (perpendicular to nail)
 - Multivariate regression evaluating predictors of time to placement
 - Level of training
 - Number of cases performed
 - Number of interlocking screws placed
 - Time since last case
 - Learning curve assessment
 - Time of each interlocking screw placement will be correlated with number of interlocking screws placed
 - Time of procedure and accuracy of placement will be analyzed in increments of 5 cases to evaluate for number of cases required to reach plateau
 - Data will be stratified by level of training

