7.2 SAMPLE SIZE CONSIDERATIONS

- Power: Based on a more recent paper from Konda et al, the average time for distal interlocking screw placement was 616 seconds in the control and 344 seconds in the distal targeting with an SD of 192 seconds. This suggests that a total of 30 patients would need to be enrolled for each cohort to detect a 44% decrease in the amount of time required for distal interlocking screw placement with the distal targeter with 90% power at 5% significance. (sealedenvelope.com power calculator on-line)
 - Estimating a 75% participation rate, we intend to enroll 60 patients (30 in each cohort – tibia and femur surgeries) that meet the sub-study criteria
 - Given that 9% of the currently enrolled patients (included in the main study) will not meet the sub-study criteria (retrograde nails instead of antegrade), we intend to enroll a total of 66 total patients for this study (includes patients for main study and sub study).

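### Five-case increments cannot give a reliable number of cases to plateau from about 33 cases per technique

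*Combined protocol and SAP*

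**What the plan says.** Section 2.0 lists as a secondary outcome a "comparison of learning curve between distal targeter and freehand techniques stratified by level of training". Section 7.1 gives the method: "Time of procedure and accuracy of placement will be analyzed in increments of 5 cases to evaluate for number of cases required to reach plateau". It adds: "Data will be stratified by level of training". Alongside this it plans a continuous analysis, "Time of each interlocking screw placement will be correlated with number of interlocking screws placed", and a multivariate regression of time to placement on training level, cases performed, screws placed and time since the last case.

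On volume, section 7.2 says "we intend to enroll a total of 66 total patients for this study", and section 3.5 says "Patients will be recruited from all full-time orthopaedic trauma faculty". Among the experience items in section 2.0 is the "number of times the surgeon has used the distal targeting system".

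The plan does not define plateau. It does not say whether cases are counted per operator, per training level or across everyone, and it does not give the number of operators or levels. *Time of procedure* is not defined either. Section 7.1 also restricts the time and accuracy comparison ("only data from surgeons who have performed both DT and FH techniques more than 5 times will be included") without saying whether this applies to the learning curve.

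**The concern.** To locate a plateau one must see performance change between early increments and then stop changing between later ones. That takes at least three increments, or 15 cases, in whatever unit is being followed. The trial is sized for a comparison of mean interlock time, and the learning curve divides the same cases by technique and again by operator or training level. Each 5-case mean is also noisy, so two neighbouring increments can look alike while learning continues.

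The outcome matters too. *Time of procedure* reads most naturally as whole-operation time, because the preceding item in section 7.1 separately names time per screw and section 5.3 lists length of surgery. Whole-operation time includes steps unrelated to distal locking.

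At stake is a figure for how many cases a surgeon needs with the device. Readers could use it for training although the data cannot support it. No primary result depends on it.

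**Working it through.** **The plan's own sample size.** Inputs from section 7.2: means 616 s and 344 s (difference 272 s), SD 192 s, 90% power, 5% significance, two-sided.

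- n per arm = 2 × (1.960 + 1.282)² × 192² / 272² = 10.5, so 11 per arm and 22 per cohort.
- 22 / 0.75 = 29.3, so 30 per cohort and 60 over the tibia and femur cohorts.
- 60 / 0.91 = 65.9, so 66.

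The stated 30, 60 and 66 reproduce. None of them sizes the learning curve.

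**Increments available.** Assuming an even split, 66 / 2 = 33 cases per technique. A cell is an operator or a training level, with equal volumes assumed.

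| Cells | Cases per technique per cell | Full 5-case increments |
|---|---|---|
| 1 (all pooled) | 33 | 6 |
| 2 | 16.5 | 3 |
| 3 | 11 | 2 |
| 4 to 6 | 8.3 to 5.5 | 1 |
| 7 or more | 4.7 or fewer | 0 |

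Pooling keeps six increments but does not trace any operator's learning. Ordered by each operator's own case number, later bins hold only the busier operators. Ordered by date, each bin mixes experience levels.

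**Noise between increments.** Standard error of the difference between two 5-case means = SD × √(2/5). The 95% half-width uses t(0.975, 8 df) = 2.306. Power is for a two-sided t-test, 5 against 5. The 192 s SD is for interlock time and stands in for the within-operator SD, which is not given; half and one and a half times that value show the range.

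| SD | Standard error | 95% half-width | Power, 136 s | Power, 272 s |
|---|---|---|---|---|
| 96 s | 61 s | 140 s | 50% | 97% |
| 192 s | 121 s | 280 s | 17% | 50% |
| 288 s | 182 s | 420 s | 10% | 26% |

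At 192 s, power for a 100 s change is 11%, and the smallest difference detectable with 80% power is 389 s. The 272 s is the difference between techniques, used only as a yardstick; 136 s is half of it.

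**What a plateau rule would return.** This is a simulation of an assumed exponential improvement from 616 s to 344 s, SD 192 s, six pooled increments, and time constants of 5, 10 and 15 cases. The true curve has less than 10% of its improvement left at case 13, at case 25, and not within 30 cases, respectively.

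- Rule: no significant difference between consecutive increments. A plateau is declared at the first comparison in 87%, 90% and 92% of runs.
- Rule: first increment not faster than the one before. It is declared at the first comparison in 16%, 23% and 29%, and by the third increment in 50%, 53% and 59%.
- Over SD 96 to 288 s, declaration at the first comparison ranges from 66% to 94% under the first rule and from 2% to 36% under the second.

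**What a continuous model gives.** Let x = log2(1 + prior uses), fitted with an operator term. The standard error of the change per doubling is SD / √(sum over operators of Σ(x − mean x)²). With SD 192 s and no prior uses:

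- Two operators with 16 cases each: about 31 s.
- Six operators with 5 cases each: the sum is 6 × 3.36 = 20.2, so 192 / √20.2 = 43 s.

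To compare like with like, mean x is 1.38 over cases 1 to 5 and 2.98 over cases 6 to 10, a span of 1.6 doublings. On that contrast the model's standard error is about 1.6 × 31 = 50 s to 1.6 × 43 = 69 s, against 121 s for two bins in one cell. The gain comes from pooling over operators and assuming a log-linear curve. It shrinks per doubling where operators start experienced: three operators with 11 cases each give 33 s from zero prior uses but 114 s from ten.

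**The case against.** The strongest reply is that the plan names no test or threshold for a plateau, so no error rate can be called a property of the plan. That stands. A reader might infer from the power figures at 192 s that a false plateau would be declared 50% to 89% of the time (one minus power at 272 s and 100 s), and that the trial would publish a learning curve that is too short. Both inferences need a non-significance rule that section 7.1 does not contain; under a no-further-drop rule, early declaration is much less frequent.

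It is also fair that the number of operators and levels is unknown, that two equal cells would leave the minimum of three increments, and that the noise depends on an SD borrowed from another measure. The shortage is therefore a range.

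Third, section 7.1 already plans a per-screw correlation and a regression on experience, so it would be wrong to say that the learning curve rests on 5-case bins alone. Those analyses use the data better, but neither estimates a plateau, so they do not rescue that figure.

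Fourth, section 2.0 treats each distal interlock as a separate outcome, so accuracy has more than five observations per bin. With two screws per case, standard errors would fall by a factor of at most √2 (121 s would become 86 s on the time scale), and by less if screws in one patient are correlated. This does not help a once-per-operation time.

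Finally, whole-operation time is a likely reading of *time of procedure*, not a stated definition, and no SD for it is given. One cannot say from the documents how much worse the analysis would be on that measure.

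**Conclusion.** The concern holds in a limited form. Section 7.1 commits to a method, 5-case increments by training level, that cannot deliver a dependable number of cases to plateau from about 33 cases per technique. With three or more equal cells there are at most two full increments, fewer than a plateau requires. With fewer cells, neighbouring increments are still hard to separate: power for a 136 s change is 17% at SD 192 s and no better than 50% over SDs of 96 to 288 s. How often the answer would be too early depends on a rule that the plan leaves open; under a non-significance rule it would be the usual result in the curves simulated. Leaving the rule open also means it could be chosen after the data are seen.

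This rests on an even split between techniques, equal volumes across cells and the 192 s stand-in. The sample-size calculation is not in error on this point, and the matter is confined to a secondary analysis.

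**What to change.** In section 7.1, replace the 5-case plateau analysis by extending the correlation and regression already planned:

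- Model interlock time against log(1 + cumulative uses of the technique), with an operator term, a technique-by-experience interaction and training level as a covariate. Adding one allows for operators with no prior uses. Treat accuracy in the same way.
- Start the distal-targeter count from the prior uses collected under section 2.0. For freehand, use the estimated total of nails placed, and say that this is not specific to the technique.
- Record an operator code with each case; section 5.3 does not list one.
- Report the change per doubling of experience with its confidence interval, label the analysis exploratory, and make no claim about a number of cases to plateau.

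This still serves the section 2.0 aim of comparing learning curves and needs no more patients. It costs the single headline figure, a wording change and one extra data item. The interval may be wide if operators enter the trial already experienced, and reporting it will make that visible.

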7.2 SAMPLE SIZE CONSIDERATIONS

- Power: Based on a more recent paper from Konda et al, the average time for distal interlocking screw placement was 616 seconds in the control and 344 seconds in the distal targeting with an SD of 192 seconds. This suggests that a total of 30 patients would need to be enrolled for each cohort to detect a 44% decrease in the amount of time required for distal interlocking screw placement with the distal targeter with 90% power at 5% significance. (sealedenvelope.com power calculator on-line)
 - Estimating a 75% participation rate, we intend to enroll 60 patients (30 in each cohort – tibia and femur surgeries) that meet the sub-study criteria
 - Given that 9% of the currently enrolled patients (included in the main study) will not meet the sub-study criteria (retrograde nails instead of antegrade), we intend to enroll a total of 66 total patients for this study (includes patients for main study and sub study).

